8.10 Medical Device Accountability

The investigator will maintain records including date of receipt, lot number and quantities of the medical device under study.

8.11 Return or Destruction of Medical Device

[figure not shown]
At completion of the study, there will be a final reconciliation of devices shipped and used. This reconciliation will be logged on the device accountability form, signed and dated. Any

Der Balgrist

discrepancies noted will be investigated, resolved, and documented prior to return or destruction of study devices. Devices destroyed on site will be documented in the study files.

9 STUDY ASSESSMENTS

9.1 Study Flow Chart

9.2 Assessments of Outcomes

9.2.1 Assessment of Primary Outcome

Bone tunnel volume will be assessed on CT. CT-scanning will be overseen by an experienced radiologist. The procedure (including pregnancy testing) is described in more detail in ACLROCS_WI_CTS defense. The DICOM (Digital Imaging and Communications in Medicine) series are converted into a single volume and cropped to include the distal femur. Subsequently, the follow-up volumes of each patient are volumetrically registered to the baseline volume by using a rigid affine mutual information algorithm [83]. An intensity-based mask of each volume is created and cropped to contain only the femoral bone tunnel. The voxel-based volume of each follow-up mask is determined and compared to the baseline volume. The procedure is described in detail in ACLROCS_WI_FemBoneTunVolCalc.

9.2.2 Assessment of Secondary Outcomes

9.2.2.1 Assessment of Patient Subjective Knee Function

IKDC SKEF, LKSS and TAS are assessed with patient filled eCRFs using online surveys on a tablet computer. The procedure is conducted by the SN.

9.2.2.1.1 IKDC Subjective Knee Evaluation Form

IKDC SKEF contains a total of 16 items. The responses to each item are scored using an ordinal method such that a score of 0 is given to responses that represent the lowest level of function or highest level of symptoms. The IKDC SKEF score is calculated by summing the scores for the individual items and then transforming the score to a scale that ranges from 0 to 100. The maximum possible item score is 87. IKDC SKEF score therefore is calculated as follows:

$$\text{IKDC SKEF Score} = \frac{\text{Sum of item scores}}{87} \times 100$$

9.2.2.1.2 Lysholm Knee Scoring Scale

LKSS contains a total of 8 items. Each item response is scored based on the table shown below. LKSS score is calculated by summing up all item scores. The range of possible total score is [0,100].

Symptoms	Options	Points
Hinken	kein	5
	leicht oder gelegentlich	3
	stark oder konstant	0
Hilfsmittel	keine	5
	Stock oder Unterarmgehstütze	2
	Belastung unmöglich	0
Blockieren	kein Blockieren und kein Gefühl des Einklemmens	15
	Gefühl des Einklemmens aber kein Blockieren	10
	gelegentilches Blockieren	6
	regelmässiges Blockieren	2
	blockiertes Gelenk bei der Untersuchung	0
Instabilität	niemals "giving way" (=einknicken)	25
	selten während des Sports oder anderer starker Anstrengung	20
	regelmässig während des Sports oder anderer starker Anstrengung (oder Teilnahme unmöglich)	15
	gelegentlich bei Alltagsaktivitäten	10
	oft bei Alltagsaktivitäten	5
	bei jedem Schritt	0
Schmerzen	keine	25
	nicht immer und leicht während starker Anstrengung	20
	deutlich während starker Anstrengung	15
	deutlich während oder nach mehr als 2 km gehen	10
	deutlich während oder nach weniger als 2 km gehen	5
	konstant	0
Schwellung	keine	10
	bei starker Anstrengung	6
	bei gewöhnlicher Anstrengung	2
	konstant	0
Treppensteigen	keine Probleme	10
	leicht eingeschränkt	6
	Stufe für Stufe	2
	unmöglich	0
Kniebeugen (in die Hocke gehen)	kein Problem	5
	leicht eingeschränkt	4
	nicht mehr als 90°	2
	unmöglich	0

9.2.2.1.3 Tegner Activity Scale

TAS contains one item. It is scored based on the following table. At surgery visit (Visit 2), preinjury activity score will be assessed.

Instructions	Choice	Score
Die folgende Frage bezieht sich auf Ihr Aktivitätsniveau. Bitte lesen sie die nachfolgende Aufstellung durch und kreuzen das HÖCHSTE Level an, das auf Sie zutrifft.	Fussball	10
	Eishockey, Ringen, Turnen, Fussball (untere Ligen)	9
	Skifahren, Badminton, Squash, Leichtathletik (Weitsprung)	8
	Handball, Tennis, Basketball, Leichtathletik (laufen), Querfeldeinlauf / Eishockey, Fussball, Squash, Weitsprung, Querfeldeinlauf	7
	Badminton, Tennis, Basketball, Skifahren, Joggen bis 5x die Woche	6
	Radfahren, Skilanglauf / Joggen auf unebenem Boden mind. 2x/Woche / Schwerarbeit (Bauarbeiter)	5
	Skilanglauf, Radfahren, Joggen auf ebenem Boden mind. 2x die Woche / Zeitweise schwere Arbeit	4
	Schwimmen / Schwimmen / Leichte körperliche Arbeiten / Gehen auf unebenem Boden	3
	Kaum körperliche Arbeit / Gehen im Wald unmöglich	2
	Überwiegend sitzend / Gehen nur auf ebenem Boden möglich	1
	Arbeitsunfähigkeit aufgrund einer Knieverletzung / Normales Gehen nicht möglich	0

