Das vordere Kreuzband verläuft im Kniegelenk von der Oberschenkelrolle zum Schienbeindach und stabilisiert zusammen mit dem hinteren Kreuzband das Kniegelenk. Durch diese Führung werden andere Strukturen des Kniegelenks wie Menisken und Knorpel gegen eine Zerstörung geschützt. Rupturen des Kreuzbandes treten häufig in Sportarten die schnelle Richtungswechsel beinhalten (z.B. Fussball, Basketball) und im Bereich Ski Alpin auf. Zur Rekonstruktion des vorderen Kreuzbandes wird meist körpereigenes Material als Transplantat verwendet. Hierzu wird das mittlere Drittel des Kniestiegenbands (Patellarsehne) mit je einem kleinen Knochenblock aus der Kniestiege und dem Unterschenkel entnommen. Alternativ können auch Beugesehnen an der Innenseite des Kniegelenks (Semitendinosus- oder Gracilisseehne) als Transplantat verwendet werden. Das Transplantat wird mittels Kniegelenkspiegelung (arthroskopisch) in Bohrkanälen im Oberschenkel respektive im Unterschenkel mit Hilfe von Schrauben oder Stiften fixiert. Die Verwendung des Kniestiegenbands bietet hierbei den Vorteil eines beschleunigten Einwachsens des Transplantats in den Bohrkanal. Jedoch können an der Entnahmestelle Komplikationen wie Schmerzen und Kniestiegenfrakturen auftreten. Da bei der Verwendung einer Beugesehne kein Knochenblock entnommen wird, ist deren Entnahme unproblematischer, der Heilungsverlauf im Bohrkanal aber oft langwieriger. Das zu testende Medizinprodukt besteht aus einem knochenwachstumsinduzierenden Knochenersatz. Dieser soll das Einwachsen des Beugesehnentransplantats in den Bohrkanal beschleunigen. Der Knochenersatz wird in das Sehnentransplantat eingefädelt und kommt nach dessen Einziehen am gelenksnahen Ende des Bohrkanals im Oberschenkel zu liegen.

Zweck dieser Studie ist es, bei insgesamt 56 Patienten den Heilungsverlauf nach Kreuzbandrekonstruktion mit der zu untersuchenden Technik, mit der herkömmlichen Methode zu vergleichen. Primär untersucht wird das Auftreten von etwaigen Komplikationen sowie die Verknöcherung des Bohrkanals, ermittelt durch radiologische Untersuchungen. Hierzu werden der Heilungsverlauf, sowie die Patientenzufriedenheit und die Kniestabilität über einen Zeitraum von 5 Jahren verfolgt.

ABBREVIATIONS

ACL	Anterior cruciate ligament
AE	Adverse Event
BPTB	Bone patellar tendon bone
BTW	Bone tunnel widening
CA	Competent authorities (Swissmedic)
CEC	Competent Ethics Committee
ClinO	Clinical Trials Ordinance
CRF	Case Report Form
CT	Computed Tomography

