4.3 Secondary Objectives

Secondary objectives are to assess patient subjective measures of knee function and objective measures of knee stability of the interventional treatment compared to the control treatment. Also the success of return to pre-injury activity level will be assessed. Additionally OCS-bone integration will be investigated.

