5.2.2.4 Tegner activity scale

The Tegner activity scale (TAS) is used to measure the change in physical activity from pre-injury to follow-up. It was designed to complement the functional outcome of the LKSS. Patient's activity is scored on a scale with 11 levels from level 0 (on sick leave/disability) to level 10 (participation in competitive sports such as soccer at a national or international elite level) [71]. Evaluated will be the difference in score from pre-injury (assessed at baseline visit) to follow-up.

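### As printed, the Tegner answer list gives ten sports two or more scores with almost nothing to mark playing level, so returning to the same sport at a lower level can score as no change

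*Combined protocol and SAP*

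**What the plan says.** Section 5.2.2.4 uses the Tegner scale to measure the change in activity from before the injury to follow-up, on 11 levels. It describes only the two ends of the scale. The top is "level 10 (participation in competitive sports such as soccer at a national or international elite level".

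Section 9.2.2.1.3 gives the single item, with an instruction, a choice and a score for each level. The instruction is "Bitte lesen sie die nachfolgende Aufstellung durch und kreuzen das HÖCHSTE Level an, das auf Sie zutrifft". The level 10 choice is the one word Fussball. The next three choices are:

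- Level 9: "Eishockey, Ringen, Turnen, Fussball (untere Ligen"
- Level 8: "Skifahren, Badminton, Squash, Leichtathletik (Weitsprung"
- Level 7: "Handball, Tennis, Basketball, Leichtathletik (laufen), Querfeldeinlauf / Eishockey, Fussball, Squash, Weitsprung, Querfeldeinlauf"

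Under section 9.2.2.1 patients complete the item on a tablet, in a procedure run by the study nurse. Section 11.4.2.5 compares the pre-injury to follow-up difference between arms with a Mann-Whitney U test. The outcome serves a secondary objective in section 4.3: "Also the success of return to pre-injury activity level will be assessed".

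**The concern.** A list that gives the same sport several scores needs wording that tells the entries apart. Without it, the instruction to choose the highest applicable level makes the lower entry redundant, because anyone who plays the sport can truthfully choose the higher one. A patient who played competitively before the injury and plays only for recreation afterwards could then choose the same row twice.

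That is the loss the return-to-activity objective is meant to detect. The sports involved are also common in this population. The German-language summary lists sports in which the injury often occurs; football comes first and the list continues "Basketball) und im Bereich Ski Alpin". All three sports sit at more than one score.

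**Working it through.** **No planned figure to reproduce.** The power table in section 11.2.1 has no Tegner column, and no sample size or detectable difference is stated for this outcome. The check is therefore an enumeration of the printed list, followed by its own scoring rule.

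**Step 1: count the entries.** Sport entries in section 9.2.2.1.3, levels 10 down to 3: 1 + 4 + 4 + 10 + 5 + 3 + 3 + 2 = 32, under 19 names. The three jogging entries are counted separately because their frequency or terrain wording distinguishes them. Of the 32 entries, 1 has a league label (football, level 9) and 0 have a competitive or recreational label.

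**Step 2: find sports at two or more scores and apply the rule.** Change = follow-up score minus pre-injury score. The third column follows the instruction literally at both visits. The fourth assumes that the lower entry is the recreational one, which the list does not say.

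| Sport | Scores | Highest row both times | Higher row, then lowest row |
|---|---|---|---|
| Football | 10, 9, 7 | 0 | 7 − 10 = −3 (from level 9: 7 − 9 = −2) |
| Ice hockey | 9, 7 | 0 | 7 − 9 = −2 |
| Skiing | 8, 6 | 0 | 6 − 8 = −2 |
| Badminton | 8, 6 | 0 | 6 − 8 = −2 |
| Squash | 8, 7 | 0 | 7 − 8 = −1 |
| Long jump | 8, 7 | 0 | 7 − 8 = −1 |
| Tennis | 7, 6 | 0 | 6 − 7 = −1 |
| Basketball | 7, 6 | 0 | 6 − 7 = −1 |
| Cycling | 5, 4 | 0 | 4 − 5 = −1 |
| Cross-country skiing | 5, 4 | 0 | 4 − 5 = −1 |

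Ten sports are affected, covering 3 + 9 × 2 = 21 of the 32 entries. Cross-country running is printed twice within level 7 and swimming twice within level 3. Those repeats cannot change a score, but they too lack any distinguishing wording.

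**Step 3: compare the two definitions of level 10.** Section 5.2.2.4 requires elite competitive sport; the choice in section 9.2.2.1.3 requires only football. A recreational footballer can truthfully choose it. This mismatch needs no assumption about the lower rows.

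**Step 4: consider inconsistent reading.** A recreational footballer whose activity has not changed, but who chooses 10 for the pre-injury state and 7 at follow-up, scores 7 − 10 = −3. The reverse order gives 10 − 7 = +3. The ambiguity can thus hide real changes (extra zeros, hence ties in the Mann-Whitney test) and can also manufacture false ones.

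**The case against.** Several objections have weight.

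- **The live form has not been seen.** The printed table was read from PDF and the eCRF screen is not in the documents, so labels could have been lost. This stands as a caveat. It is unlikely to explain the finding, because other qualifiers in the same table survive: the league note, the athletics disciplines, the construction-worker example and the slashes.
- **Patients may work out the order.** Football at 10, then lower leagues at 9, then football again at 7 suggests a ranking, and the study nurse could clarify. This stands in part: misreading is possible, not certain. But no clarifying instruction is written, and the other nine sports offer no such cue.
- **The documents do not reproduce the published scale.** A reader might infer that labels were removed from it. That cannot be checked here.

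Three stronger readings are tempting and should not be adopted.

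- One might say that the form records only which sport is played. It does not: level 9 has a league label, and levels 6 to 4 carry frequency, terrain or workload wording.
- One might say that return to activity is certainly overstated in both arms and that any arm difference shrinks toward zero. Step 4 shows that errors can run either way, and nothing in the documents says how many of the 56 patients would be affected.
- One might extend the harm to the adjusted analysis in section 11.4.2.1. There the pre-injury Tegner score is one of four candidates, is retained for the preliminary model only at p < 0.2, and belongs to a secondary model.

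**Conclusion.** The concern holds for the list as printed. The level 10 choice does not match the protocol's own definition, and ten sports have two or more scores with a single league label among them. A fall in playing level within one sport can score as zero. The size of the hidden loss, 1 to 3 levels for an affected patient, rests on the assumption that the lower row is the recreational one.

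The likely consequence is reduced sensitivity, with added noise and ties, in a secondary outcome, and a possible overstatement of return to pre-injury activity. Both arms use the same form and patients are blinded (section 6.3.2), so the documents give no reason to expect a bias favouring one arm. The primary CT endpoint is untouched. The point is worth correcting because the correction is cheap; it does not threaten the trial's main conclusion.

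**What to change.** 1. Compare the live eCRF item with the table in section 9.2.2.1.3. If the eCRF already carries the labels, only the protocol table needs correcting.
2. If it matches the printed table, state the level of participation in every choice, in both places, following the wording of the scale that section 5.2.2.4 cites. Level 10 should agree with section 5.2.2.4, and no sport should appear at two scores without wording that separates the entries.
3. Use the identical form for the pre-injury assessment at Visit 2 and at every follow-up.
4. If patients have already answered the unlabelled form, ask their pre-injury level of participation again, so that both ends of the difference use the same wording. Report those answers as recalled after surgery.

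The cost is an edit to one eCRF item and one protocol table, handled as an amendment under section 2.10, with no extra visits. The small downside is the added recall in step 4, which arises only if patients have already answered.

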9.2.2.2 Assessment of Knee Stability

KT-1000 Arthrometer-, Lachman- and Pivot-shift testing are performed by the PI. All tests are performed first on the involved and secondly on the normal contralateral side.

KT-1000 Arthrometer testing is performed with the patient in supine position on a firm examination table. The knee is flexed to an angle between 20° and 35°. The thighs rest on a support platform. The KT-1000 Arthrometer testing device is then strapped to the anterior aspect of the tibia. After zeroing of the machine, tibial anterior displacement is measured. The measurement is performed once, and the results are noted in millimeters on the respective eCRF.

Lachman testing is performed by manual anterior displacement of the tibia in 15° flexion. The calf is grasped with one hand and quickly pulled anteriorly, while the other hand constrains the movement of the thigh. The test is performed once. The results are noted in the respective eCRF using the grading system displayed below.

Grade	Displacement
0	<3 mm
1	3 - 5 mm
2	>5 mm

For Pivot-shift testing, the anteriorly subluxated tibia head is repositioned manually. While a manual force is applied for internal rotation, valgisation and axial pressure, the knee is flexed manually from full extension. The rolling-gliding motion is assessed. The test is performed once. The results are noted in the respective eCRF using the grading system displayed below.

Grade	Finding
0	Normal
1	Glide
2	Clunk
3	Gross clunk with locking

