5.2.2.1 KT-1000 Arthrometer Test

The KT-1000 Arthrometer Test measures anterior displacement of the tibial plateau on the femur at a specific force. Its output variable is defined as the difference in full millimeters between the tibial displacement of the ACL reconstructed knee and the normal contralateral side [73].

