5.2.2.2 Lachman Test

The Lachman test measures anterior displacement conducted manually by the clinician. It is graded as the difference from the normal contralateral side as 0 (<3 mm), 1 (3 to 5 mm), or 2 (>5 mm) [74].

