6.3.3 Other Methods of Minimizing Bias

Patient subjective knee function will be assessed using German versions of validated questionnaires [69, 72]. KT-1000 arthrometer testing provides the means to objectively measure anterior knee stability [80].

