9.3 Procedures at Each Visit

9.3.1 Screening (Visit 1)

Eligible patients will be informed about the ongoing study by the PI or by an involved practitioner, and will be handed out study patient information including informed consent form.

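### Knee stability: KT-1000 is read once per knee over an unfixed flexion range, and the PI does all three tests with only the patient blinded, so there is avoidable reading noise and a risk of observer bias at follow-up

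*Combined protocol and SAP*

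**What the plan says.** Stability is a secondary objective (section 4.3), measured by three tests: KT-1000, Lachman and pivot shift (section 5.2.2).

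- **Examiner.** Section 9.2.2.2: "KT-1000 Arthrometer-, Lachman- and Pivot-shift testing are performed by the PI". Section 9.3.3 has the PI repeat the preoperative examination at follow-up, and the later visits refer back to it.
- **Replication.** For KT-1000, "The measurement is performed once, and the results are noted in millimeters on the respective eCRF". For Lachman and for pivot shift, "The test is performed once".
- **Conditions.** KT-1000 may be taken anywhere between 20 and 35 degrees of flexion (9.2.2.2). Section 5.2.2.1 refers to a specific force, but neither section gives its value.
- **Resolution.** Section 5.2.2.1: "Its output variable is defined as the difference in full millimeters between the tibial displacement" of the two knees. Lachman has three grades and pivot shift four (5.2.2.2, 5.2.2.3).
- **Blinding.** Section 6.3.2 blinds the patient. It says that the operator cannot be blinded, nor can the practitioner who evaluates the images at follow-up and for safety. It does not mention a stability examiner.
- **Stated safeguard.** Section 6.3.3: "KT-1000 arthrometer testing provides the means to objectively measure anterior knee stability". It names no safeguard for the two manual tests.

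**The concern.** There are two separate issues.

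The first is precision. The KT-1000 outcome is a difference between two single readings, so the reading error of both knees enters it in full. An unfixed flexion angle lets measurement conditions vary between knees, visits and patients. Repeat readings would reduce this error within the same visit.

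The second is observer bias. Lachman and pivot shift are judged by hand, and KT-1000 is a hand-operated device. If the examiner knows the arm, a small systematic lean becomes a treatment difference that neither sample size nor repetition removes. The main funder licenses patents on which study personnel are co-inventors (section 2.6), so stability results from an examiner who was not shielded from allocation would be hard to defend.

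**Working it through.** **1. Reproduce the plan's figure.** Inputs from section 11.2.1 for KT-1000: 25 per group, two-sided alpha 0.05, difference 2 mm, SD 1.7 mm, printed effect size 0.88, printed power 0.84. The test is Mann-Whitney (11.4.2.4). Using the noncentral t with n multiplied by the Mann-Whitney efficiency 3/π, an effect size of 0.88 gives power 0.845, which matches. The table's own inputs give 2/1.7 = 1.18 and power 0.978. The printed effect size therefore does not follow from them; that is a separate matter, and both values are carried below.

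**2. Gain from three readings per knee.** Let e be the error SD of one reading. It is not in the documents, so 0.5, 0.75 and 1.0 mm are assumed. Errors are taken as independent between readings. The planning variance of the side-to-side difference is 1.7² = 2.89 mm², of which 2e² is reading error. Averaging three readings removes two thirds of 2e². The shift implied by the printed effect size is 0.88 × 1.7 = 1.496 mm.

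| e (mm) | 2e² | removed | variance left | SD (mm) | variance cut | power at 1.496 mm | power at 2 mm |
|---|---|---|---|---|---|---|---|
| single reading | – | – | 2.89 | 1.70 | – | 0.845 | 0.978 |
| 0.5 | 0.50 | 0.333 | 2.557 | 1.60 | 12% | 0.886 | 0.988 |
| 0.75 | 1.125 | 0.75 | 2.14 | 1.46 | 26% | 0.933 | 0.996 |
| 1.0 | 2.00 | 1.333 | 1.557 | 1.25 | 46% | 0.982 | >0.99 |

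These are upper bounds for each assumed e. Error from strapping and positioning that is shared by repeat pulls in one set-up does not average out.

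**3. Rounding.** Section 5.2.2.1 attaches full millimetres to the difference. Rounding once adds 1/12 = 0.083 mm², and 0.083/2.89 = 2.9%. The SD goes from 1.70 to √2.973 = 1.72 mm. In a Mann-Whitney simulation at 1.496 mm, power was 0.840 unrounded and 0.834 rounded. If the literature SD of 1.7 mm already comes from rounded readings, the added loss is zero.

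**4. Effect of an examiner lean.** There is no true difference, 25 per group, and the size of the lean is assumed.

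| Test and SD (11.2.1) | lean between arms | lean/SD | false-positive rate |
|---|---|---|---|
| KT-1000, 1.7 mm | 0.25 mm | 0.147 | about 8% |
| KT-1000, 1.7 mm | 0.5 mm | 0.294 | about 17% |
| KT-1000, 1.7 mm | 1.0 mm | 0.588 | about 51% |
| Pivot shift, 0.71 | 0.2 grade | 0.282 | about 16% (t approximation) |

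These show sensitivity. They do not estimate a bias that is present.

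**5. Could the PI know the arm?**
- The PI assesses adverse-event severity (9.2.5.1), and section 6.3.2 says that the practitioner doing safety assessment cannot be blinded.
- The PI is responsible for recording data and for their correctness and completeness (12.1.1, 12.2.1). These data include the femoral tunnel diameter (9.2.4.3), which is 9 to 9.5 mm in one arm and 8 to 8.5 mm in the other (8.3), so it reveals the arm.
- The allocation card is resealed and kept in the patient's file (7.3, 9.3.2.3.2).

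No section withholds the allocation from the PI. None says that the PI operates, or examines knowing the arm.

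**6. Which visits?** The preoperative examination (9.3.2.2) precedes intraoperative randomization (9.3.2.3.2), so there is no arm to know at baseline. The bias risk is confined to follow-up.

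**The case against.** The strongest reply is that noise does not threaten these outcomes. The plan prints power of 0.84 to 0.99 for the three tests, and the table's own KT-1000 inputs give about 0.98. They are secondary outcomes, and the reading error is unknown. That stands: averaging is a cheap gain in precision, not the repair of a power failure.

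A second reply is that one constant examiner avoids between-examiner variance, which a rota with the PI as fallback would add while also mixing shielded and unshielded readings. The other team member mentioned, in section 9.3.1 ("by the PI or by an involved practitioner"), is given only the role of informing patients at screening. Nothing shows that this person is trained in the tests or absent from theatre. This stands too, and it limits what can be asked for on blinding.

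A reader might infer more than the documents support:
- *That the PI is unblinded because the PI judges each event's relation to the device.* Section 9.2.5.1 assigns only severity to the PI; device relationship is listed without an assessor. The PI's knowledge of the arm remains an inference.
- *That the results are biased.* The documents show an uncontrolled risk, not a bias that has occurred.
- *That Lachman and pivot shift lose information by rounding to grades.* The grades are the defined scales of these tests.
- *That whole-millimetre recording costs about 6% of the KT-1000 variance.* That needs each knee to be rounded separately (2/12 mm², 5.8% of 2.89). Section 5.2.2.1 puts full millimetres on the difference, which gives 2.9% at most.

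**Conclusion.** The point holds in two limited parts.

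**KT-1000 precision.** A single reading over a 15-degree flexion range adds avoidable noise. Three readings per knee would lower the SD from 1.7 mm to at best 1.60, 1.46 or 1.25 mm for assumed single-reading error SDs of 0.5, 0.75 or 1.0 mm with independent errors. The true gain cannot be derived from the documents and may be smaller. Rounding is negligible.

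**Observer bias at follow-up.** The risk is real and uncontrolled, and greatest for the two manual tests, to which the KT-1000 safeguard in section 6.3.3 does not extend. It rests on the inference that the PI can learn the arm: the documents do not say so outright, but nothing prevents it. Assumed leans of 0.25 to 1.0 mm on KT-1000 would take the false-positive rate from 5% to between about 8% and 51%.

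The baseline examination and the primary CT outcome are not affected.

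**What to change.** 1. **Section 9.2.2.2, KT-1000.** Take three readings per knee at one stated flexion angle and one stated force, the same for both knees, and analyse the side-to-side difference of the means. Change the full-millimetre definition in section 5.2.2.1 to match; otherwise the two sections will conflict.
2. **Follow-up visits only (section 9.3.3 and the visits that refer to it).** Do the stability tests before images, operation notes or the allocation card are opened. Section 9.3.3 already lists the examination before radiography, so this fits the visit.
3. **Examiner.** Where a trained team member who was not in theatre is already available, let that one person examine the patient at every follow-up visit, and record the examiner in the eCRF. Otherwise, report the Lachman and pivot-shift results as assessed by an examiner who was not blinded.

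The cost is a few minutes per visit and wording changes in the sections named. A separate examiner also needs some scheduling. Keeping one person per patient avoids examiner changes between visits, but several examiners across the trial would still add some between-examiner variance. If nobody suitable is on the team, a separate blinded examiner would mean adding a trained assessor; the reporting statement in item 3 is the alternative that needs no extra staff.
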